3.7 Intervention		
3.8 Study Timetable	10	
4. Planned Analyses	11	
5. Dissemination of Findings	11	
6. References	12	

1. Background and Rationale

The majority of those who serve in the UK armed forces do well after they leave¹. Military service, particularly combat experience, can, however, have adverse effects and these are of concern for the armed forces, other government departments, service personnel and veterans, and their families. Successive UK governments have been accused of neglecting veterans, with reports that homelessness², imprisonment³, unemployment and alcoholism are the fate of many⁴. It is estimated that around 4% of British military veterans meet the criteria for PTSD⁵. The financial and social impact is considerable⁶. Many veterans with PTSD struggle in their transition to civilian and family life, are unable to work and in receipt of long-term incapacity benefits⁷.

Only a limited proportion of people with mental health problems seek professional help. Among military populations this is true of veterans as well as serving personnel, though to a lesser extent⁸. Engaging veterans in mental health treatment programmes remains challenging due to stigma, perceived weakness in acknowledging emotional difficulties, and military macho cultures⁹. Most studies have found that informal sources of help such as family, friends and clergy are preferred^{10, 11, 12}.

In military and veteran populations, recent trials of the first-line trauma-focused interventions Cognitive Processing Therapy (CPT) and Prolonged Exposure (PE) have shown clinically meaningful improvements for many patients with PTSD^{13, 14}. However, non-response rates have been high, many patients continue to have symptoms, and trauma-focused interventions only show marginally superior results compared with active control conditions¹⁵. There is a need for improvement in existing PTSD treatments and for the development and testing of novel treatments¹⁶, including more intense interventions for those who have not responded to less intense interventions.

The Welsh Veterans' NHS service was founded in 2010 to assess and treat military veterans with mental health difficulties. It received over 542 referrals in 2014-2015, an increase of 152 on the previous year. Sixty four percent of those assessed were diagnosed with PTSD and, by the end of the year, 139 had begun out-patient psychological treatment

Veterans' NHS Wales uses evidence-based trauma focused psychological therapy to treat PTSD, including CPT, PE and Eye Movement Desensitisation Reprocessing therapy¹⁷, as part of an integrated multiagency approach to improve general health and functioning¹⁸. Despite this, and consistent with the literature described above, outcomes following trauma-focused psychological therapy have been modest, with high levels of attrition and only limited improvements in PTSD symptoms. Those veterans with treatment resistant PTSD continue to report difficulties due to their symptoms, affecting their occupational, interpersonal and social functioning. Approximately 60% of veterans with PTSD engage in a course of outpatient treatment with Veterans' NHS Wales. Many, however, drop out of therapy early or report only a modest improvement on their overall symptoms (approximately a third describe significant improvements in their symptomatology, a third modest improvements and a third no improvement or drop out of therapy).

There is, therefore, an urgent need to identify effective treatments for military veterans who do not respond to, or are unable to engage with, current first line treatments. Modular motion-assisted memory desensitisation and reconsolidation (3MDR)¹⁹ is a new treatment that aims to reduce cognitive avoidance and augment engagement with therapy. 3MDR is based on known therapeutic principles of virtual reality exposure therapy²⁰ and eye

movement desensitization and reprocessing (EMDR)²¹, embedded in a novel context in which the patient walks on a treadmill whilst interacting with a series of self-selected images that are displayed on a large screen. Exposure by virtual reality, enhanced with walking, music and high affect pictures, eliminates cognitive avoidance during exposure and promotes presence. This is an important distinction between 3MDR and traditional trauma focused techniques which are sedentary; patients learn how to move through their avoidance by, literally, approaching their traumatic memories.

In 3MDR, a dual task is used to facilitate desensitisation and reconsolidation of the emotional content of the traumatic event that is captured on a deployment related photograph. This is congruent with working memory theory, which has been used to explain the therapeutic mechanism of EMDR²². According to this theory, working memory has limited resources; if a dual task (for example, following a specific object with your eyes) uses some of those resources, less memory will be available for other memory processes, which in turn will make the recollection of memories less vivid and less affect-laden. In 3MDR, the dual task is different from most EMDR treatments. Instead of making eye movements (or alternative bilateral stimulation) alone, numbers need to be called out whilst the patient is also walking, thereby optimally taxing working memory.

Preliminary results from research conducted by the originators of 3MDR in the Netherlands regarding the efficacy of 3MDR in veterans with treatment resistant, combat-related PTSD are promising. A pilot study¹⁹ showed a decrease in PTSD symptoms and no dropout, with the two participants positive about the treatment. No adverse effects were reported and the time is now right to explore the potential efficacy of 3MDR further.

2. Aims and Objectives

The main aim of the proposed research is to determine whether 3MDR is able to reduce traumatic stress symptoms in British military veterans with treatment-resistant, combat-related PTSD, to a significantly greater degree than a waiting list.

The main objective is to answer the following research questions:

1. For British military veterans with treatment-resistant, operationally-related PTSD, does 3MDR reduce symptoms of PTSD as measured by the CAPS5 to a significantly greater degree than a waiting list? (Main research question)

2. For British military veterans with treatment-resistant, combat-related PTSD, what is the impact of 3MDR on quality of life, functioning, symptoms of depression, symptoms of anxiety, insomnia, alcohol and illicit substance use and perceived social support? (Secondary outcomes)

3. Is 3MDR acceptable to British military veterans with treatment-resistant, combat-related PTSD and those delivering the intervention as measured by qualitative semi-structured interviews?

4. What is the likely effect size of 3MDR?

5. What factors may impact efficacy and successful roll-out of 3MDR for treatment-resistant, combat-related PTSD, if 3MDR is shown to be efficacious? (Mechanism and process evaluation)

6. What is the behavioural response of the 3MDR sessions in terms of stress and cognitive processing during different dual task phases and how can this guide us in optimal design of the intervention and a Phase III definitive trial? (Mechanism evaluation)

7. Can examination of the integrity of the study protocol, trial recruitment rate, self-report outcome measures, clinician administered outcome measures, randomisation procedure, treatment integrity and acceptability enhance decision making in planning a Phase III definitive trial?

8. Is a Phase III definitive RCT indicated and feasible?

3. Methods

3.1 Study design

[figure not shown]
The study will be an exploratory single blind randomised parallel group controlled trial with nested mechanistic and process evaluation to assess fidelity, adherence and factors that influence outcome.

3.2 Setting

The School of Healthcare Sciences at Cardiff University has a Motek GRAIL system, which will be used for implementation of this study. The Motek Gait Real-time Analysis Interactive Lab (GRAIL) system uses an instrumented dual-belt treadmill, a motion-capture system and synchronized Virtual Reality (VR) environment, which comprises a 180° projection screen with 4 projectors and a surround sound system. The system is controlled by means of 6 computers in an integrated network using D-flow software. This is a control software suite that provides real-time data streams between many types of integrated hardware. The 3MDR module was designed to run in D-flow and therefore the intervention can be delivered comprehensively in the lab in Cardiff. The only extra equipment required is a Zephyr[™] BioHarness[™] 3 physiological monitor which measures multiple physiological parameters: Heart Rate (HR), Breathing Rate (BR), Temperature, Posture, and Activity Level and can be integrated with the GRAIL system through a Bluetooth-based data acquisition system. The sensor will be used for physiological status monitoring. The Motek company will install hardware and software required for this study and will provide the technical support as well as the training in the use of the system. For further reference please see: http://www.motekmedical.com/products/grail-gait-real-time-analysis-interactive-lab/ http://www.zephyranywhere.com/products/bioharness-3

Figure 1: GRAIL system with a standard virtual environment displayed (left) and running the 3MDR protocol (right).

The GRAIL system will be able to record data continuously during each session at a high sampling rate (100 frames per second) and these data are stored as a digital file. Data recorded during a session will include information about 3MDR events such as phase transitions; repeated measurements of the score on the subjective units of disturbance (SUD) scale; physiological parameters from the sensor such as heart rate; and gait parameters from the instrumented treadmill such as walking speed and distance and ground reaction forces to calculate step width. Data will, therefore, be accessible for further analysis using Matlab software; a high-level programming environment to explore and visualise data. This is used to calculate gait parameters through the phases from the treadmill speed and ground reaction force data. Matlab will be used to create individual session profiles of the physiological (HR, BR, HR Variability)²³ and motor control (walking speed, cadence and step width variability)²⁴ response to the intervention through the phases and extract summary statistics to describe changes in these responses over time. Response over time through the phases of key parameters will be plotted and explored statistically using Pearson's correlation coefficients and cross-correlations²⁵. Step width variability is suggested to provide insight into changes in cognitive demand and improvements in performance. Cognitive demand is expected to be greatest in the early stage of treatment when the emotional response is high (as demonstrated by HR variability) and during multi-task phases of the protocol.

3.3 Sample size

Although a standard power calculation is not appropriate for a Phase II exploratory trial we believe it appropriate to use a power calculation based on a previous study of TFCBT for PTSD²⁶ to inform our sample size and ensure it is adequate. The calculation suggests that for an 80% chance of detecting a mean 15 point difference on the Clinician Administered PTSD Scale between 3MDR and waiting list at a 0.05 confidence level assuming a standard deviation of 15.18, 17 subjects in each group will be needed. Allowing for a conservative estimate of a 20-25% drop out, an extra 4 subjects will be recruited to each arm representing a total proposed sample size of 42.

For the qualitative study, the sample size will be guided by preliminary analysis and constant comparison (comparing and contrasting themes from other interviews) during each data collection phase, until the research team is satisfied that there is data saturation and no new themes which are important to the research question arise²⁷. However, it is helpful to have a guide to sample size for study planning. Based on previous research²⁸, we propose that interviews will be conducted with around 10 participants, purposively sampled, and all five therapists.

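### Adding 4 to 17 per arm covers 19% drop-out, not the stated 20-25%; a minor error with a small effect on power

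*Protocol*

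**What the plan says.** Section 3.3 of the protocol gives a two-step calculation. The first step sets the number to be analysed: "17 subjects in each group will be needed" "for an 80% chance of detecting a mean 15 point difference on the Clinician Administered PTSD Scale", "at a 0.05 confidence level" and "assuming a standard deviation of 15.18". The second step adds the allowance for losses: "Allowing for a conservative estimate of a 20-25% drop out, an extra 4 subjects will be recruited to each arm", which brings the total to 42.

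The same section says that a standard power calculation does not suit an exploratory Phase II trial, but that this one is used to inform the sample size and to check that it is adequate. Section 4 plans an intention-to-treat ANCOVA with the baseline score as covariate. Section 3.3 takes no credit for that adjustment.

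**The concern.** A drop-out rate describes what fraction of randomised participants is lost. To end with n completers at drop-out d, one randomises n/(1-d). Multiplying n by (1+d) gives too few, because the allowance is then a percentage of the smaller, final number. The protocol's 4 extra per arm looks like the second calculation.

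At stake is whether the stated sample size does what the sentence says: absorb 20-25% drop-out and still leave the 17 per arm that the protocol says it needs. The allowance is called conservative, so a reader will take it that 17 completers per arm are protected across the whole range.

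**Working it through.** **Inputs (all from section 3.3 unless noted).** Difference 15; SD 15.18; alpha 0.05; power 80%; 17 per arm to be analysed; drop-out 20-25%; 4 added per arm; total 42. Sidedness is not stated. Two-sided is assumed, because one-sided gives 13 per arm (normal formula) or 13.4 (t-test) and does not reproduce 17.

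**Step 1: reproduce the 17.**
- Standardised difference: 15/15.18 = 0.988.
- Normal formula: n = 2(1.960 + 0.842)²/0.988² = 16.08, rounded up to 17. This reproduces.
- The t-test solution is 17.09, so 17 per arm gives 79.8% by t-test and 82.1% by the normal formula.

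**Step 2: reproduce the 4.**
- As a share of completers: 4/17 = 23.5%, inside 20-25%. Likewise 17 × 1.20 = 20.4 and 17 × 1.25 = 21.25, which bracket 21.
- As a share of those randomised: 4/21 = 19.0%, below the range.
- The total is consistent: 2 × 21 = 42.

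**Step 3: completers expected from 21 per arm, and numbers needed to keep 17.**

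| Drop-out | Remaining per arm | Needed per arm to keep 17 | Total |
|---|---|---|---|
| 20% | 21 × 0.80 = 16.8 | 17/0.80 = 21.25, so 22 | 44 |
| 25% | 21 × 0.75 = 15.75 | 17/0.75 = 22.67, so 23 | 46 |

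The expected shortfall against 17 is 0.2 per arm at 20% and 1.25 per arm at 25%.

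**Step 4: power at those numbers, two-sided, unadjusted.** The normal formula is Φ(0.988 × √(n/2) − 1.960); the t-test uses the noncentral t distribution.

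| Per arm | Normal formula | t-test |
|---|---|---|
| 17 (stated requirement) | 82.1% | 79.8% |
| 16.8 (20% drop-out) | 81.7% | 79.3% |
| 15.75 (25% drop-out) | 79.2% | 76.5% |

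If each participant drops out independently, so that the numbers remaining vary at random, average t-test power from 21 per arm is 78.8% at 20% and 75.8% at 25%, close to the values at the expected numbers.

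**Step 5: what the planned ANCOVA could recover.** The protocol gives no baseline-outcome correlation r. Assume that 15.18 is the unadjusted SD, and replace it by 15.18 × √(1 − r²) in the t-test calculation. Power then returns to 80% at 25% drop-out when r is about 0.29, and at 20% drop-out when r is about 0.14.

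**The case against.** A reader might infer from the failed allowance that 42 participants do not deliver 80% power. The protocol's figures do not support that without qualification. The 17 follows from the normal formula, and by that formula power at 20% drop-out is 81.7%, still above target, and at 25% it is 79.2%. Judging power by the t-test mixes methods, and by that test even the full 17 per arm gives only 79.8%. At 20% drop-out the allowance error therefore costs about half a point.

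Nor can one say that the design has no slack. The planned analysis adjusts for baseline and section 3.3 takes no credit for it; a correlation of about 0.3 would restore 80% even at 25% drop-out. That correlation is an assumption, so the gain cannot be counted as established, but it cannot be ruled out either.

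It is also tempting to quote the chance that both arms keep at least 17: 0.586² = 34% at 20% drop-out and 0.367² = 13% at 25%. These mostly reflect binomial variation around an expected shortfall of 0.2 to 1.25 per arm, and they overstate the harm.

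Finally, the trial is exploratory and its power calculation is only meant to inform the size. That lowers the priority, but it does not make the sentence right: the calculation is offered as evidence of adequacy, and the allowance in it is misstated. Analysing by intention to treat does not remove the point either, since section 3.3 itself adds participants to make up for drop-outs.

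**Conclusion.** The drop-out sentence is wrong as written, and the error is minor. Twenty-one per arm covers 19.0% drop-out, which lies below both ends of the stated range. Holding 17 per arm would take 44 participants at 20% and 46 at 25%, that is, 2 or 4 more than planned.

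The effect on power is small: at most 0.7 points below 80% at 20% drop-out (t-test; none by the normal formula), and 0.8 to 3.5 points below at 25%. Only the last figure, at the upper end of the range and under an unadjusted t-test, is material. All of this rests on a two-sided test, the protocol's own difference and SD, equal drop-out in both arms and drop-outs contributing nothing to the analysis. The first step of the calculation and the total of 42 are otherwise consistent.

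**What to change.** Keep 42 and correct the sentence in section 3.3, for example: 21 per arm allows for 19% drop-out; at 25% drop-out about 16 per arm remain, and unadjusted two-sided t-test power is about 76%. Alternatively, restate power for the planned ANCOVA at the expected numbers remaining, and give the assumed baseline-outcome correlation with its source. In either case state that the test is two-sided.

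The cost is one corrected sentence and no extra participants. The downside is that the stated drop-out allowance and power look slightly less favourable. If the sponsor prefers to keep the 20-25% wording and the 17 completers, the total must rise to 46 to cover the whole range.

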3.4 Inclusion/exclusion criteria

Wide eligibility criteria will be used to ensure good external validity. Given the high rate of co-morbidity of PTSD and other conditions such as depression and substance misuse, individuals with co-morbidity will be included if they satisfy the other inclusion/exclusion criteria and PTSD is considered the primary diagnosis. This is consistent with NICE guidance and will result in a pragmatic trial.

Inclusion criteria will be: Aged 18 or over; Informed consent; Meet DSM5²⁹ criteria for combat-related PTSD; treatment-resistance defined as prior receipt of a trauma focused psychological treatment without loss of PTSD diagnosis.

Exclusion criteria will be: Psychosis; DSM5 severe major depressive episode; Substance dependence; Change in psychotropic medication within one month; Suicidal intent; Inability to walk at a normal pace for 30-45 minutes on a treadmill.

3.5 Recruitment and consent

British military veterans and soliders that are currently serving in the armed forces who attend the Veterans' NHS Wales Service and/or Cardiff and Vale Traumatic Stress Service who are considered to be likely to fulfil the inclusion criteria for the study will be asked by a clinician involved in their care if they are willing for their details to be passed on to the research team. Veterans who have been discharged from the clinic will be sent a letter from the clinician inviting them to take part in the study and if the veteran is interested to contact the clinician. If clinicians don't hear back from the veteran within two weeks, they can follow up with a second letter but not a telephone call and if the veteran doesn't respond they will not be contacted again.

The clinical team will do all the necessary checks before sending out letters in order to avoid distress to the veteran and or their families.

The research team will contact potential participants and provide them with an information sheet about the study. They will be given at least 24 hours to consider this before being asked if they require further information or any questions answered. If potential participants wish to proceed, arrangements will be made to enter them into the study.

Informed consent will always be obtained before the initial assessment proceeds. The member of the research team who is conducting the assessment will check that the participant has read and understood the information sheet. They will check –

a. whether the participant has any questions arising from the information sheet and answer any that do arise.

b. that the participant understands their participation is voluntary and that they are free to withdraw at any time without giving any reason, without their medical care or legal rights being affected.

c. whether the participant agrees to their GP being informed of their participation in the study.

d. whether the participant agrees to take part in the study.

The member of the research team who is conducting the assessment will then request the participant to complete the consent form.

All work will be conducted in full compliance with the Data Protection Act.

3.6 Outcome measures

The primary outcome will be symptoms of PTSD measured by the Clinician Administered PTSD Scale for DSM5 (CAPS5)³⁰. The CAPS5 is a 29 item structured interview for assessing PTSD diagnostic status and symptom severity. The CAPS is the gold standard in PTSD assessment and can be used to make a current (past month) or lifetime diagnosis of PTSD or to assess symptoms over the past week. Items correspond to the DSM5 criteria for PTSD. Previous versions of the CAPS have excellent reliability and excellent convergent and discriminant validity, diagnostic utility, and sensitivity to clinical change³¹.

Secondary outcome measures will include self-report measures that are routinely collected by Increasing Access to Psychological Therapies (IAPT) services in England and veteran services at present (PTSD Checklist³² for traumatic stress; Work and Social Adjustment Scale³³ for quality of life/functional impairment; Patient Health Questionnaire-9³⁴ (PHQ-9) for depression; General Anxiety Disorder-7³⁵ (GAD-7) for anxiety; AUDIT-O³⁶ for alcohol use) and changes in sleep will be measured by the insomnia severity index (ISI)³⁷. In addition, the Multidimensional Scale for Perceived Social Support³⁸ will be used to assess perceived social support. Changes in health related quality of life will be measured by the EQ5D-5L³⁹.

PTSD Checklist (PCL-5) - The PCL-5 is a 20 item scale which aims to index self reported symptoms of PTSD as described in the Diagnostic and Statistical Manual of Mental Disorders (DSM-5). The PCL -5 is based on an earlier version of the PCL, which is widely used and well validated³².

The Work and Social Adjustment Scale (WSAS) is a self-report measure, which assesses the impact of a person's mental health difficulties on their ability to function in terms of work, home management, social leisure, private leisure and personal or family relationships. The WSAS is the outcome measure of choice for evaluating improvement in functioning in IAPT services. The WSAS has been demonstrated to show good reliability and validity and is sensitive to change³³.

The PHQ-9 is a widely used reliable and well-validated brief self-report measure of depression³⁴. It is the outcome measure of choice for evaluating improvement in depressive symptoms in IAPT services⁴⁰.

The GAD-7 is a widely used reliable and well-validated brief self-report measure of anxiety³⁵. It is the outcome measure of choice for evaluating improvement in anxiety symptoms in IAPT services⁴¹.

*The AUDIT-O*³⁶ contains 10 multiple choice questions on quantity and frequency of alcohol consumption, drinking behaviour and alcohol-related problems or reactions over the preceding 3 months.

The Insomnia Severity Index (ISI) is a widely used 7-item self-report questionnaire assessing the nature, severity, and impact of insomnia. It has been shown to be reliable and valid in terms of detecting insomnia and in measuring treatment response in clinical patients³⁷.

The Multidimensional Scale for Perceived Social Support (MSPSS) is a widely used12-item Likert scale measuring the subjective assessment of adequacy of social support from family, friends, and partners⁴¹. The reliability, validity, and factor structure of the MSPSS have been demonstrated with a number of populations^{38,42,43}.

*The EQ5D-5L*³⁹ is a widely used instrument in health economic analysis and recognised by NICE as an appropriate measure for health related quality of life. The questionnaire provides a simple descriptive profile, which translates to a single utility score for health status. The first part of the instrument identifies the extent of perceived problems – across five levels - in each of five life dimensions: mobility; self-care; usual activities; pain and discomfort; and anxiety and depression. The responses to each of the five questions are used to generate a utility score for self-rated health status on a 0-1 scale, where 0 represents the worst possible health state and 1 the best possible health state. The second part is a visual analogue scale, which allows the responder to indicate their current health status on a 0-100 scale.

An experienced researcher blind to randomisation will conduct all assessments. The initial assessment will ensure that the inclusion criteria are satisfied. Demographic and other background data will be collected along with completion of all the outcome measures. Participants will then be asked to monitor their symptoms for two weeks. The baseline assessment of all the outcome measures will occur after this; those who continue to fulfil the inclusion criteria will be randomised to one of the two groups: 3MDR or wait list for 12 weeks followed by 3MDR. Follow up will occur 12 and 26 weeks after randomisation. This will involve re-administration of all the outcome measures. At 26 weeks participants will be asked to participate in semi-structured interviews to elicit their experience and views of the programme. Progress will be monitored with the PCL-5, PHQ-9 and GAD-7 at each treatment session.

